The overall objective of the present research is to use ecological momentary assessment (EMA), a real-time, naturalistic data collection method, to prospectively study the impact of reduced cannabis use on functional outcomes in heavy cannabis users. EMA addresses several limitations of traditional assessment techniques by enhancing ecological validity, minimizing memory bias, and enabling examination of the impact of context on participants' behavior. Our central hypothesis is that reductions in frequency and quantity of cannabis use will lead to positive changes in cannabis users' functional outcomes. The rationale for this research is that it will provide real-time data concerning the impact of reductions in cannabis use on functioning and will support efforts to include reductions in illicit drug use as a valid outcome measure in pharmacotherapy studies (Tiffany et al., 2011; Donovan et al., 2011).

Contingency management (CM) will be used to promote reductions in frequency and quantity of cannabis use. CM is an intensive behavioral therapy that is highly effective at producing short-term reductions in illicit drug use. Moreover, we have developed a novel approach that leverages mobile technology and recent developments in cannabis testing to make daily CM for cannabis more portable and feasible. We have pilot-tested this approach with heavy cannabis users and found that it is an acceptable and feasible method to reduce cannabis use. The present research will use this technology in conjunction with state-of-the-art EMA methods to study the impact of reduced cannabis use on key functional outcomes.

We will pursue the following specific aims during the R21 phase:

R21 Aim 1: Refine the study procedures and the CM reinforcement schedule to ensure that a majority of participants will be adherent, find the study procedures acceptable, and substantially reduce their frequency and quantity of cannabis use.

Milestone 1: The majority (i.e., $\geq 65\%$) of participants will be adherent and rate procedures as acceptable.

Milestone 2: We will identify a CM reinforcement schedule that reliably produces $\geq 50\%$ reductions in frequency and quantity of cannabis use among at least half of the heavy cannabis users enrolled.

R21 Aim 2: Examine the association between days of cannabis use and total amount of cannabis used.

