We have now collected feasibility and acceptability data from 4 heavy cannabis users on the use of the saliva test as part of the mobile CM for cannabis protocol (PRO00072366; Beckham, Adkisson et al., manuscript submitted). Participants were trained to self-administer the test. They were then asked to videotape themselves twice daily (at least 8-hours apart) while taking the test during a 1-week *ad lib* period followed by 4-weeks of mobile CM. During each video recording, participants: 1) started a video recording session using the smartphone; 2) showed the unused test strip to the camera; 3) swabbed his/her cheek while on camera; 4) placed the strip on a flat surface for 5 minutes; and 5) recorded the final result with the camera. Saliva sticks were numbered to ensure they were not reused or substituted. Videos were uploaded and transmitted to our secure server using the app described above. Two raters independently reviewed each video and indicated if the saliva test was positive or negative. In 1% of videos, coordinators identified a problem (i.e., control strip was not legible) and the sample was rated as invalid (participants were given the benefit of the doubt and were paid in these rare instances). Agreement between raters was excellent (100%) as was agreement between participant self-report and saliva results (96%).

B.5. Preliminary Pilot Data on Mobile CM for Cannabis

As noted above, 4 participants have completed the mobile CM for cannabis protocol to date. All of the heavy cannabis users who completed the 4-week mobile CM for cannabis protocol reduced their cannabis use. On average, participants reduced the number of days they used cannabis from 17.5 days to 10.3 days per month, representing a 41% reduction in frequency of cannabis use on average. These preliminary findings demonstrate that: (1) we can recruit and retain heavy cannabis users in the proposed mobile CM protocol; (2) mobile CM for cannabis is feasible and accepted by heavy cannabis users; and (3) mobile CM produces a range of reductions in frequency of daily cannabis use (18-93%) that make it an ideal platform from which to study the impact of reduced frequency of cannabis use on functional outcomes.

C. R21 APPROACH

C.1. R21 Aims and Milestones

[figure not shown]

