In Aim 1 of the R21 phase of the project, we will evaluate the acceptability of the study procedures and further refine the CM reinforcement schedule to ensure that a majority of participants will be adherent, find the study procedures acceptable, and substantially reduce their cannabis use. In Aim 2, we will examine the association between frequency of cannabis use and total amount of cannabis consumed per week.

C.2. Overview of the R21 Study Design and Participant Flow

Figure 1 depicts the R21 study design and participant flow. Interested participants that meet initial eligibility criteria during a phone screen will complete an in-person baseline assessment to determine final eligibility. We anticipate that we will need to complete 24 baseline assessments to enroll a final sample of 18 eligible participants. Eligible participants will complete 2 weeks of *ad lib* monitoring during which time they will use cannabis typically to establish baseline patterns of use. Following the 2-week *ad lib* period, participants will complete the 6-week mobile CM for cannabis protocol aimed at

reducing their cannabis use. Afterwards, participants will return to the laboratory to return equipment and to complete an in-person 8-week follow-up.

Figure 1. R21 Study Design & Participant Flow

C.3. R21 Inclusion/Exclusion Criteria

Inclusion criteria include: (a) cannabis use other than ingested cannabis (i.e., edibles) on ≥ 40 of past 90 days; (b) ability to speak and write fluent English; (c) 18-80 years of age; and (d) willingness to attempt to temporarily reduce cannabis use. Participants will be excluded if they: (a) expect to have an unstable medication regimen during the study; (b) are currently receiving non-study CUD treatment; (c) meet criteria for serious mental illness (e.g., bipolar disorder, schizophrenia); (d) become imprisoned; (e) become hospitalized for psychiatric reasons; (f) become pregnant; (g) report imminent risk for suicide or homicide; or (h) meet criteria for a substance use disorder other than CUD or tobacco.

C.4. Recruitment & Enrollment

We estimate that we will need to recruit 24 participants to meet our overall goal of enrolling 18 eligible participants. Participants will be recruited from the community and from outpatient clinics at Duke

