Saliva testing will occur contemporaneously with EMA alarms. Participants will be required to video record themselves taking a saliva test each time they are alarmed to complete EMA, i.e., three times per day. During the *ad lib* phase of the monitoring, we will ask participants to do a self-initiated EMA and saliva test if they use marijuana. Participants will be asked to begin a reading when beginning to use marijuana. An alarm will be set for 60 minutes later. At the alarm, participants will complete a saliva test. Participants will be paid \$5 each day if they do a self-initiated reading. During the active CM phases of the study, if a participant tests negative at each time point, he/she will be reinforced for abstinence that day. In addition, participants will be granted one “free day” per week in which they can use cannabis and still be reinforced if they upload their saliva tests. Please note that participants are reinforced separately for uploading both positive and negative saliva tests (they receive \$2.50 per upload, regardless of cannabis use), enabling us to compare participants’ saliva test results with their self-report. Participants will be given half of the required saliva screening strips at their screening visits, and then will be mailed remaining strips about halfway into the treatment period.

C.6.3. Cohort 1: Protocol Refinement. After the first 6 participants have completed the mobile CM for cannabis protocol, we will ask each of them to rate the acceptability of the procedures. We will also conduct interviews with participants to identify and resolve any issues that may have contributed to poor adherence and/or poor response to the CM procedures. A summary of this feedback will then be evaluated by the study team (i.e., Co-PIs, Co-I’s, Consultant, and computer programmer) and incorporated into the revised protocol. We will also evaluate compliance data and calculate the reduction in cannabis use that participants achieved during CM to determine if further adjustments to the reinforcement schedule are needed.

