C.6.4. Cohort 2: Further Protocol Refinement. Once the protocol and/or reinforcement schedule have been modified based on information learned from the first cohort, we will administer the revised mobile CM for cannabis protocol to a second cohort of heavy cannabis users ($n=6$) and repeat the evaluative measures described above. Any additional modifications needed to improve adherence, acceptability, or efficacy of the mobile CM for cannabis protocol will be implemented at this time. We have found this second small cohort particularly helpful in previous treatment development studies, as it allows for careful evaluation of changes in procedures and reinforcement schedules.

C.6.5. Cohort 3: Milestone Assessment. Once the EMA protocol and CM reinforcement schedule have been finalized based on information learned from cohort 2, we will administer the final version of the

protocol to a third cohort ($n=6$) to determine if our first two milestones have been met. Our first milestone will be to demonstrate that a majority (i.e., 4/6) of cohort 3 participants will be adherent to the study protocol and rate the study procedures as acceptable. Protocol adherence will be defined as completing the baseline assessment, 8-week follow-up assessment, and 1 or more EMA assessments per day (total ≥ 56) for the duration of the 8-week EMA protocol. Acceptability will be assessed with a questionnaire specifically designed for this study. Our second milestone will be to demonstrate that we have identified a reinforcement schedule that reliably produces $\geq 50\%$ reductions in frequency and quantity of cannabis use in at least half of the participants in cohort 3 (i.e., 3/6). By aiming to reliably produce clinically meaningful reductions in frequency and quantity of cannabis use in at least half of the participants, we will maximize our ability to study the impact of reduced cannabis use on key functional outcomes during the R33 phase of the project. To evaluate if this milestone has been met, we will calculate the percentage reduction in bioverified abstinent days and overall cannabis quantity by comparing the *ad lib* monitoring period to the mobile CM period.

C.7. Association between Frequency of Use and Total Amount of Cannabis Consumed (R21 Aim 2)

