In Aim 2 of the R21, we will examine the association between number of bioverified abstinent days and self-report of total quantity of cannabis use per week. Quantity of cannabis consumed during EMA assessments will be calculated as the inverse of the self-reported average number of joints made from 1 gram of cannabis (joints/gram) consumed per EMA period, as this approach has been demonstrated to reliably assess cannabis quantity (van der Pol, Liebregts, Graff, Korf, van den Brink & van Laar, 2013). We will use van der Pol et al.'s (van der Pol, Liebregts, Graff, Korf, van den Brink & van Laar, 2013) methods to assess cannabis potency *via* self-report, and total THC load will be calculated as joints/gram x potency. Participants will also be prompted at the end of each day (~ 11 pm) to estimate the total amount of joints/gram they used that day. Our third milestone involves examining the association between frequency of cannabis use (i.e., days) and total amount of cannabis consumed per week based on participants' EMA data on quantity of cannabis use. By tracking the total amount of cannabis that participants use, we will be well-positioned to account for such an effect in the R33 analyses. To assess this milestone, we will calculate days since last use for each report of cannabis use. We will use count-adjusted (i.e., negative binomial or Poisson) MLM to model the equivalent number of joints/gram smoked on a given day as a function of days since last use. We anticipate the association of latency between days since last use and amount consumed will be small (i.e., Cohen's $d \leq 0.10$).

C.8. Additional Bioverification of Cannabis Use.

At three time points (screening, end of the *ad lib* period, end of treatment), we will ask participants to provide a urine sample. These urine samples will be sent to Lab Corp for creatinine normalization analyses to determine cannabinoid concentrations. Measurement of cannabinoid concentration will allow analyses of reduced cannabis use.

D. R33 APPROACH

D.1. Overview of the R33 Study Procedures

If the proposed R21 milestones are met, the R33 phase of the project will be used to conduct a fully powered test of our central hypothesis that reductions in frequency and quantity of cannabis use will

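### C.6.5 scores the Milestone 2 frequency criterion on abstinent days, which contradicts the reduction-in-use target it is meant to test

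*Combined protocol and SAP*

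**What the plan says.** The Specific Aims set Milestone 2 as a CM schedule that reliably produces 50% or greater "reductions in frequency and quantity of cannabis use among at least half of the heavy cannabis users enrolled". Section C.6.5 narrows this to cohort 3: 50% or greater "reductions in frequency and quantity of cannabis use in at least half of the participants in cohort 3 (i.e., 3/6"). The closing sentence of the same section gives the calculation: "we will calculate the percentage reduction in bioverified abstinent days and overall cannabis quantity", ad lib period against CM period.

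The milestone has consequences. Section D.1 states: "If the proposed R21 milestones are met, the R33 phase of the project will be used to conduct a fully powered test".

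Elsewhere, change in frequency is computed on days of use. Section B.5 reports that pilot "participants reduced the number of days they used cannabis from 17.5 days to 10.3 days per month" and calls this a 41% reduction. Section E.2 defines weekly frequency for R33 as days used. Section C.7 (R21 Aim 2), however, also takes bioverified abstinent days as its frequency measure.

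**The concern.** The target and its scoring rule move in opposite directions. When a participant uses less, abstinent days go up, and the percentage reduction in abstinent days is negative. Taken literally, the rule fails those who succeed.

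The obvious repair, reading reduction as increase, does not work either. A percentage change in abstinent days has a different denominator from a percentage change in days of use, so the two agree only when a participant uses on exactly half of baseline days.

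The quantity component points the right way and can be scored for a daily user. It does not rescue the rule, because frequency and quantity are both required. With six participants and a bar of three, reclassifying one person can change whether the milestone is met.

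**Working it through.** **Inputs**
- Ad lib period: 2 weeks, 14 days (C.2).
- CM period: 42 days, since "participants will complete the 6-week mobile CM for cannabis protocol" (C.2).
- Eligibility: "cannabis use other than ingested cannabis (i.e., edibles) on ≥ 40 of past 90 days" (C.3). There is no upper limit, so daily users are eligible and may have no abstinent ad lib days.
- Abstinent day, as described for the CM phases: "if a participant tests negative at each time point, he/she will be reinforced for abstinence that day" (C.6.2).
- Pilot days of use per month: 17.5 falling to 10.3 (B.5).

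**The plan's own percentage.** Percentage reduction = (baseline - CM) / baseline. On days of use, (17.5 - 10.3) / 17.5 = 41.1%, which reproduces the stated 41%. The pilot figure was therefore computed on days of use.

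**The C.6.5 formula on one participant.** Take 10 of 14 ad lib days and 15 of 42 CM days with use.
- Use: 10/14 × 7 = 5.0 days per week; 15/42 × 7 = 2.5 days per week; reduction 50%.
- Abstinent share: 4/14 = 0.286; 27/42 = 0.643. Score: (0.286 - 0.643) / 0.286 = -125%.
- If raw counts were compared instead of rates: (4 - 27) / 4 = -575%. C.6.5 does not say which is meant.

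**General form.** Let u be the baseline share of days with use and r the fractional cut in use. The abstinent share goes from 1 - u to 1 - u(1 - r), so the literal score is -r·u/(1 - u). This is negative for every real reduction and undefined at u = 1.

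Literal score for a participant who halves use, as rates per 14 days:

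| Ad lib use days of 14 | Abstinent days, before and after | Literal score | Reduction in use |
|---|---|---|---|
| 7 | 7 to 10.5 | -50% | 50% |
| 10 | 4 to 9 | -125% | 50% |
| 13 | 1 to 7.5 | -650% | 50% |
| 14 | 0 to 7 | undefined | 50% |

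To score +50% literally from 40/90 days, the abstinent share would have to fall from 50/90 to 25/90. Use would then rise from 44% to 72% of days. If all six participants halved use, six of six would meet the frequency threshold on days of use and none would under the literal rule.

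**Sign reversed.** The score becomes r·u/(1 - u), so the 50% bar requires r ≥ 0.5(1 - u)/u.
- u = 40/90: u/(1 - u) = 0.8. A halving scores 0.5 × 0.8 = 40% and misses; a 62.5% cut is needed.
- u = 10/14: u/(1 - u) = 2.5. A 20% cut scores 50% and passes.
- u = 13/14: u/(1 - u) = 13. A cut of about 4% passes.
- u = 14/14: zero denominator.

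Pilot means, for illustration only: with an assumed 30-day month, abstinent days go from 12.5 to 19.7, up 58%; with 28 days, from 10.5 to 17.7, up 69%. Use fell 41% in either case. The reversed metric errs in both directions and is most lenient for the heaviest users.

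**The case against.** The strongest reply is that this is a slip of wording. C.6.5 itself states the target correctly, the Specific Aims agree, C.6.3 has the team calculate the reduction in cannabis use for cohort 1 (repeated for cohort 2), and B.5 and E.2 work in days of use. A schedule that pays for abstinence cannot be meant to reduce abstinent days, so staff may well have scored days of use. The missing reference to rates is minor, since a percentage comparison of unequal periods is naturally read that way. The sign-reversed rule is written nowhere, and the pilot illustration applies a mean of four people, under a different schedule, to a criterion judged per participant.

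Most of this stands as an account of intent. It does not remove the point. The C.6.5 sentence is the only one that says how Milestone 2 is evaluated, and nothing corrects it. Because C.7 also uses abstinent days for frequency, a reader could reasonably keep that metric and change only its direction, and that version misclassifies too.

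Several stronger readings are tempting but unsupported:
- **That cohort 3 was mis-scored or the decision to proceed was wrong.** D.1 says R21 data were evaluated and CM procedures modified, but no section reports how Milestone 2 was scored or its result.
- **That the milestone fixes the reinforcement schedule.** C.6.5 finalises the schedule after cohort 2 and then gives it to cohort 3. The milestone tests it.
- **That the milestone result is still owed in a report.** No section says so.
- **That E.2 shares the error.** It already defines frequency as days used per week.

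**Conclusion.** The point holds as an error in the written scoring rule. The frequency half of the Milestone 2 calculation contradicts its target in the same section and the days-of-use convention in B.5 and E.2. Taken literally, no participant who halves use can reach the 50% threshold, and a participant without abstinent ad lib days cannot be scored. With the sign reversed, the cut in use needed to pass runs from 62.5% at the eligibility minimum to about 4% at 13 of 14 days, against an intended 50% throughout.

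The arithmetic assumes that the periods are compared as rates and that every day can be classed as use or abstinent; only the pilot illustration needs an assumed month length. The sentence gates R33 through the milestone, but Milestone 2 does not enter the R33 analyses. Whether the error had any practical effect cannot be determined from the documents.

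**What to change.** Replace the last sentence of C.6.5 with a rule that scores two quantities, ad lib (14 days) against CM (42 days):
- the percentage reduction in the proportion of days that are not bioverified abstinent, that is, days of use, compared as rates;
- the percentage reduction in cannabis quantity per week.

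State one rule for days with missing tests and apply it in both periods. Such days should not count as non-use by default, because that would favour passing and would weaken the bioverification standard.

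Add a statement of how Milestone 2 was actually scored for cohort 3. If the abstinent-day formula was used in either direction, re-score the six participants. If days of use were scored, saying so is enough. E.2 needs no change.

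The cost is one replacement sentence, a short statement on scoring, and at most six recalculations from data already collected.
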